- Results of 12 month surveillance biopsies
- Lipid panels and use of lipid lowering medications at 1 year after transplant
- Incidence of MI and CHF at 1 and 3 years after transplant

- Incidence of wound infection at 1 year after transplantation
- Incidence of lymphocele at 1 year after transplantation
- Plasma concentrations of S-adenosyl homocysteine (SAH) and S-adenosyl methionine (SAM) Plasma concentrations of endothelial dysfunction markers (symmetric and asymmetric dimethyl arginine (SDMA, ADMA), L-arginine, L-citrulline, L-ornithine, cysteine, and homocysteine over the observation period
- Plasma concentrations of bioactive lipids (HODEs, HEPEs, HETEs, and prostaglandins) over the observation period
- Plasma protein patterns

Data analysis: The incidence of graft loss, patient death, and acute rejection will be compared by chi squared analyses. Patient and graft Kaplan-Meier survival curves will be compared by log rank test. We hypothesize there will be no statistically significant difference between the treatment arms. As this is a pilot study, it was not statistically powered to detect subtle differences in outcome. All continuous variables such as serum creatinine, cGFR, serum lipids, WBC, platelets, etcetera will be compared by student's t test. Any other dichotomous variables will be compared by chi squared analysis.

1 Background

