Two prospective randomized trials (A2306 and A2307) have demonstrated that everolimus combined with steroids and low dose Neoral with (A2307) or without (A2306) basiliximab induction result in excellent 1 year outcomes (1). In 2002 we adopted an immunosuppressive regimen using Rapamune and reduced dose Neoral without steroids using induction therapy with Thymoglobulin. Since employing this regimen our acute rejection rate within the first year post-transplant has been between 7% and 10% for any given calendar year. However, many patients need to have their Rapamune discontinued due to drug related side effects or compliance difficulties related to the noon dosing (when most other medications are taken at 8 am and 4 pm). We feel strongly that use of an alternative drug to Rapamune in such cases is necessary. Use of Zortress in this setting would be ideal, however, no data currently exists concerning the use of Zortress with Neoral in a steroid free maintenance immunosuppression regimen following Thymoglobulin induction. Thus we propose this pilot study primarily to verify Zortress efficacy using our established immunosuppressive protocol. Secondarily we are interested in characterizing the Zortress drug related side effect profile to enable us in the future to exploit any favorable differences between Zortress and Rapamune.

2 Purpose and rationale

Our center's renal transplant immunosuppression protocol has consisted of Thymoglobulin and steroid induction for 5 doses only, with early initiation of Rapamune® (Sirolimus) and then Neoral for nearly a decade now. We do observe a significant amount of adverse events in our patient population, with many of these potentially related to the Sirolimus. The combination of "half-dose" cyclosporine (early C2 levels around 800 to 1000 ng/ml) allows us to minimize calcineurin inhibitor toxicity and its combination with the mTOR drug Sirolimus provides excellent protection against acute rejection in our renal transplant recipients. Our earlier experience with Everolimus and the recent publications describing renal recipients' outcomes with this drug, suggest to us that our patients may do better on Everolimus than Sirolimus (1,2). For our center, this pilot study would be very straightforward as the only difference in medication from our current well established protocol would be the randomization to either Rapamune®, our current standard of care, or Zortress®, the study drug.

3 Objectives

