The patient population will be all adults (18-75 years of age) who receive a living donor or deceased donor renal transplant as a first or subsequent renal transplant procedure only (no extra-renal organ transplant recipients). We will invite any patient who would normally be considered for our current Sirolimus®/ Neoral® protocol with Thymoglobulin® and steroid induction to consent for this pilot study and then undergo randomization post-operatively if the transplant surgeon anticipates normal early graft function. If there were significant concerns for prolonged graft dysfunction, then the patients will not be invited into the pilot study. Invited patients would include anyone currently not on steroids prior to transplantation, and those with no known intolerance to any of the drugs mentioned. Patients must also be willing to perform the expectations of the study protocol reliably.

This will be a single center pilot study performed at The Ohio State University Comprehensive Transplant Center. Our center performs approximately 100 to 110 living donor and 90 to 100 deceased donor renal transplants per year. If we assume that at least 150 patients per year qualify for the study, then a conservative estimate of 75 enrolled patients a year is possible. We would propose to enroll a total of 60 patients over 12 months, and then follow these patients for a complete 3 years. We will randomize 2:1 Zortress to Sirolimus using a random number generator.

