6.2 Treatment arms

Patients will be assigned to one of the following “n” treatment arms in a ratio of 2:1; Zortress or Sirolimus started on POD 0, with Solumedrol 500 mg IV in OR as induction, then 5 doses of Thymoglobulin starting morning of POD 1 at 1.25 mg/dose (rounded to nearest 25 mg) with rapid steroid taper over five doses. Neoral will be introduced as renal function recovers, usually starting on POD 2. We will enroll a total of 60 patients.

- Zortress and Neoral, with Thymoglobulin induction and perioperative steroids
- Rapamycin and Neoral, with Thymoglobulin induction and perioperative steroids

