10.1.2 Statistical hypothesis, model, and method of analysis

The primary endpoint will be a composite endpoint of graft survival (non-death censored) and biopsy proven acute rejection at 1 year.

Secondary endpoints at 6 months, 1, 2 and 3 years will include: graft survival and patient survival/death at 2 and 3 years, rate and grade of acute cellular rejection, rate of acute antibody mediated rejection, rate of new donor specific antibody formation, estimated CrCl by MDRD, lipid control as determined by requirement for anti-lipid medications and average levels with and without medications, ability to maintain initial immunosuppressive medications and reason for switch if required, wound complications as determined by need for wound packing, infection treatment with antibiotics, presence of hernia on exam and requirement for hernia repair, as well as presence of symptomatic lymphocele, and New Onset Diabetes After Transplant as determined by need for new oral or sustained Insulin medication.

Statistical analysis will be performed on SPSS or STATA software with dichotomous variables evaluated by Chi-Squared analysis, continuous variables by Student's T-Test, non-parametric outcomes will be assessed by Wilcoxon rank sum test (Mann-Whitney U test). Kaplan-Meier survival curves with log rank tests will be used to determine a difference in graft and patient survival over time.

Safety data will include patient and graft survival, biopsy proven acute rejection, and hospital admissions.

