10.3 Sample size calculation

Due to the fact that the sample size is 60 patients, this will be a pilot study that is exploratory in nature, and therefore not powered to show statistical difference.

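### Chi-squared is the only test named for binary outcomes, with no small-count method or confidence interval, although expected rejection counts are below 5 in both arms (minor)

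*Combined protocol and SAP*

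**What the plan says.** Section 10.1.2, under the analysis of the primary objective, defines the endpoint: "The primary endpoint will be a composite endpoint of graft survival (non-death censored) and biopsy proven acute rejection at 1 year". For the method it has "dichotomous variables evaluated by Chi-Squared analysis", and Section 10.2.1 repeats this for the secondary endpoints. The synopsis (Data analysis) applies the same test to the components: "The incidence of graft loss, patient death, and acute rejection will be compared by chi squared analyses". Log-rank tests are added only for graft and patient survival, so rejection and the composite rest on chi-squared alone. No exact test, small-expected-count rule, continuity correction, significance level or confidence interval is specified.

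On size, Section 6.2 states "We will enroll a total of 60 patients" and Section 5 states "We will randomize 2:1 Zortress to Sirolimus using a random number generator". Section 1 gives the only event rate in the documents: "our acute rejection rate within the first year post-transplant has been between 7% and 10% for any given calendar year". Section 10.3 describes the trial as "therefore not powered to show statistical difference". Section 6.5.6 nevertheless makes a statistically significant difference in the primary outcome, together with the treating physicians' opinion that it reflects efficacy, the ground for considering early termination. Section 10.5 schedules an interim look at 6 months.

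**The concern.** The chi-squared p-value is a large-sample approximation, and the protocol's own figures show in advance that event counts will be too small for it to be dependable near 0.05. The plan also leaves open whether a continuity correction applies. In the sparsest tables that choice alone decides whether a result is called significant.

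Two things are at stake. A handful of events in the 20-patient arm could be declared a significant difference and so satisfy the statistical half of the early-termination condition. And a bare p-value says nothing about how large a disadvantage of Zortress the data still allow. That is what a reader needs when the stated aim is equivalency (Section 3.1) and the stated expectation is non-inferiority (Section 10.5).

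**Working it through.** The plan contains no calculation to reproduce. The inputs are:
- N = 60 (Section 6.2) and 2:1 allocation (Section 5), implying 40 v 20. The arm sizes are not printed.
- First-year rejection rate 7-10% (Section 1).
- Assumed, because not stated: two-sided 0.05, and Pearson's test without correction unless noted.

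**Expected events** (arm size x rate, equal rates in both arms)
- Rapamune: 20 x 0.07 = 1.4 to 20 x 0.10 = 2.0.
- Zortress: 40 x 0.07 = 2.8 to 40 x 0.10 = 4.0.
- An expected count of 5 in the smaller arm needs 5/20 = 25%, or 15 events in total.

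The documents give no rate for graft loss, death or the composite. At an assumed 2-5% for graft loss or death, the 20-patient arm expects 0.4-1.0 events. At an assumed 12-15% for the composite it expects 2.4-3.0. All are below 5.

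**Borderline tables** (Zortress v Rapamune)

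With a and b events in the arms of 40 and 20, Pearson's statistic is 60 x [a(20-b) - b(40-a)]² / [40 x 20 x (a+b) x (60-a-b)].
- 0/40 v 2/20: 60 x 80² / (40 x 20 x 2 x 58) = 4.14.
- 7/40 v 0/20: 60 x 140² / (40 x 20 x 7 x 53) = 3.96.

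| Table | Pearson | Yates | Fisher |
|---|---|---|---|
| 0/40 v 2/20 | 0.042 | 0.204 | 0.107 |
| 7/40 v 0/20 | 0.047 | 0.118 | 0.084 |

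The first table can be checked by counting. If two events occur in all, chance puts both in the 20-patient arm with probability C(20,2)/C(60,2) = 190/1770 = 10.7%. That is Fisher's p-value; Pearson reports 4.2%.

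**Type I error.** All 41 x 21 tables were enumerated under Binomial(40, p) and Binomial(20, p), and the probabilities of those with p-value below 0.05 were summed by direction.

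| Common rate | Pearson: Zortress worse / Rapamune worse / total | Fisher: Zortress worse / Rapamune worse / total |
|---|---|---|
| 7% | 0.47% / 3.4% / 3.8% | 0.14% / 2.0% / 2.1% |
| 8.5% | 0.85% / 3.0% / 3.8% | 0.31% / 2.2% / 2.5% |
| 10% | 1.25% / 2.7% / 4.0% | 0.55% / 2.25% / 2.8% |

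With Yates' correction the total is 0.5-0.8% over this range.

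**How often the choice matters.** Pearson and Fisher fall on opposite sides of 0.05 in about 1.7% of null trials at 7% and 1.2% at 10%, almost all of it from the two tables above. The first has null probability 190 x 0.07² x 0.93⁵⁸ = 1.4% at 7%, and 0.4% at 10%.

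**Power if Zortress is worse** (assumed 25% v 8.5%): Pearson 31.7%, Fisher 28.6%.

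**The case against.** The best defence is that little depends on p < 0.05 here. The trial is an exploratory, unpowered pilot. Harm on Zortress is watched by monthly clinical review without a p-value (Section 10.2.2). Early termination needs the physicians' judgement as well as significance (Section 6.5.6). Pearson's test keeps its overall error below 5%, and the choice of test rarely changes the verdict. All of this stands, and it is why the point is minor.

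Two stronger readings are tempting, and neither is supported.

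- **That chi-squared is unsafe because it hardly detects Zortress being worse, and Fisher's test cures this.** The two directions are unequal (0.85% v 3.0% at 8.5% events), but the cause is 2:1 allocation with sparse events. Fisher's test is less sensitive still in that direction (0.31%), and its ratio between directions is wider: about 7:1 (2.2/0.31) against 3.5:1 (3.0/0.85).
- **That the primary endpoint itself is as sparse and lopsided as the extreme cases.** At 5% events Pearson's split is 3.9% v 0.1%, but 5% lies below the documented rejection rate. The composite adds graft loss and death to rejection, so its rate should be no lower than that of rejection. By 15% the split is 2.5% v 2.0%.

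What remains is that the test is not fully specified, its borderline p-values are unreliable at the expected counts, and no interval is planned.

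**Conclusion.** The point holds as a minor one. Expected rejection counts are 1.4-2.0 and 2.8-4.0. Results such as 0/40 v 2/20 are significant or not depending on a choice the plan leaves open (0.042, 0.204 or 0.107). A reader might infer that false-positive findings are inflated. They are not: Pearson's total error is 3.8-4.0% at 7-10% events.

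The practical consequence is confined to about 1.2-1.7% of null trials, and matters chiefly because significance of the primary outcome enters the early-termination condition. These figures assume exactly 40 and 20 evaluable patients, equal true rates of 7-10%, two-sided 0.05 and no continuity correction. Composite, graft-loss and death rates are not in the documents, so their counts are illustrative. That a difference test cannot by itself establish equivalence is a separate and larger matter.

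**What to change.** In the synopsis (Data analysis) and Sections 10.1.2 and 10.2.1:

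1. Make the risk difference, Zortress minus Rapamune, with a score-type 95% confidence interval the main result for the 1-year composite and its components.
2. Replace chi-squared with an exact test (Fisher's or an unconditional exact test) wherever an expected count is below 5. At 40:20 that means fewer than 15 events, or fewer than 15 non-events, in total. State the significance level and sidedness.
3. Name one interval method, Miettinen-Nurminen or Newcombe, in advance, because they can differ on the tables at issue. For 0/40 v 2/20 the Miettinen-Nurminen statistic at zero difference is 4.14 x 59/60 = 4.07, above 3.84, so that interval excludes zero. Newcombe's upper limit is -0.100 + √(0.0876² + 0.0721²) = +0.013, using the Wilson upper limit 0.0876 for 0/40 and lower limit 0.0279 for 2/20 (0.100 - 0.0279 = 0.0721), so that interval includes zero.

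The cost is a few sentences and no new data; SPSS and Stata, the packages the plan names, both provide Fisher's test. The downside should be stated in the plan. Fisher's test is conservative (size 2.1-2.8% at 7-10% events), leaves the directional asymmetry in place, and lowers power against Zortress being worse from about 32% to 29% in the 25% v 8.5% example. That direction should therefore be judged from the confidence interval, not from the p-value.

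### With 2:1 allocation, the pooled-variance Student's t-test is miscalibrated for continuous secondary outcomes if the arms differ in spread; Welch's test, with skewed outcomes logged, is the better default

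*Combined protocol and SAP*

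**What the plan says.** The synopsis (Data analysis) states: "All continuous variables such as serum creatinine, cGFR, serum lipids, WBC, platelets, etcetera will be compared by student's t test". Sections 10.1.2 and 10.2.1 both specify "continuous variables by Student's T-Test", then add that "non-parametric outcomes will be assessed by Wilcoxon rank sum test (Mann-Whitney U test". The synopsis has no such addition, and no section says which outcomes count as non-parametric or what would move an outcome from one test to the other.

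Section 5 sets the allocation: "We will randomize 2:1 Zortress to Sirolimus using a random number generator". Section 6.2 sets the size: "We will enroll a total of 60 patients". Together these imply about 40 Zortress and 20 Rapamune patients.

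The documents do not mention Welch's test, unequal variances, a variance check, expected SDs or a significance level. Student's two-sample test is ordinarily the pooled-variance test, and nothing in the text gives it another meaning.

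**The concern.** The pooled-variance test estimates one common SD, weighted towards the larger arm. With equal arms, a difference in spread does little harm. At 40:20 the standard error is wrong whenever the SDs differ. It is too small if the 20-patient Rapamune arm is more variable, so chance differences look significant too often. It is too large if the 40-patient Zortress arm is more variable, so real differences are missed.

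The outcomes concerned include creatinine, estimated GFR, lipids, white cells and platelets. The background section gives the side-effect profile of Zortress as the second purpose of the study, with a view to using any advantage it has over Rapamune. Readers will look to these comparisons for that.

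**Working it through.** **Plan's own figure.** There is none to reproduce. The total of 60 is given without alpha, power, effect size or SD.

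**Inputs.** From the documents: 60 patients at 2:1, so n1 = 40 (Zortress) and n2 = 20 (Rapamune). Assumed: two-sided 5% level; normal data; Zortress SD = 1 and Rapamune SD = r, with r from 0.5 to 2.

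**Large-sample formula.** Type I error of the pooled test ≈ 2·[1 − Φ(1.96·√k)], where

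k = [(n1 + n2·r²)/(n1 + n2)]·(1/n1 + 1/n2) ÷ (1/n1 + r²/n2).

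The numerator is the variance of the difference that the pooled test assumes. The denominator is the true one.

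- r = 0.5: k = 0.05625/0.0375 = 1.500; 1.96·√k = 2.400; error 1.6%
- r = 0.8: k = 0.0660/0.0570 = 1.158; 1.96·√k = 2.109; error 3.5%
- r = 1.25: k = 0.0891/0.1031 = 0.864; 1.96·√k = 1.821; error 6.9%
- r = 2: k = 0.150/0.225 = 0.667; 1.96·√k = 1.600; error 11.0%

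With n1 = n2 the formula gives k = 1 for every r.

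**Simulation at 40/20** (normal data, equal means; repeat runs agree to about 0.1 point):

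| SD ratio Rapamune:Zortress | Student | Welch |
|---|---|---|
| 0.5 | 1.8% | about 5% |
| 0.67 | 2.6% | about 5% |
| 0.8 | 3.6% | about 5% |
| 1 | 5.0% | about 5% |
| 1.25 | 6.8% | about 5% |
| 1.5 | 8.6% | about 5% |
| 2 | 11.1% | about 5% |

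Welch was between 4.9% and 5.1% throughout. At 30/30 Student's test stays at 5.0% to 5.2% over the same ratios, so the distortion comes from the 2:1 split. An assumed 20% loss (32/16) changes almost nothing.

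**Power, normal data.** With equal SDs and a 0.8 SD effect, power is 81.8% (Student) v 81.1% (Welch). With the Zortress arm more variable (ratio 0.67, difference 0.783 Zortress SDs), it is 90.4% v 94.3%.

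**Spread that grows with the mean.** This was simulated as lognormal data with the same log-SD in both arms.

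- Equal means: Student's type I error is 4.7% to 5.0% for log-SDs of 0.3 to 0.7, so there is no inflation.
- Rapamune raises the level 1.5-fold, untransformed data: power is 80.5% (Student) v 73.7% (Welch) at log-SD 0.5, and 50.4% v 37.0% at 0.7. If Zortress is the higher arm, Welch gains instead.
- Rapamune 1.5-fold at log-SD 0.5, analysed on the log scale: 83.0% v 82.3%.

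**Skew and unequal spread together** (equal means; log-SD 0.7 on Rapamune, 0.5 on Zortress): type I error is 8.2% (Student) v 6.8% (Welch). Welch alone does not fully correct it.

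**The case against.** The strongest objection concerns mechanism. Triglycerides and creatinine usually vary more where they run higher, and a reader might infer that a drug which raises them will therefore inflate false positives. That does not follow. If spread depends only on the mean, the SDs differ only when the means differ, and then the null is false. The lognormal runs with equal means confirm this. The table of error rates applies only if the arms differ in spread while sharing a mean, and the documents give no SDs to show whether they would.

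A second objection is that Section 10 already offers Wilcoxon, for which skewed outcomes are natural candidates. That is fair as a limit on scope: outside the synopsis, the plan does not commit every continuous outcome to a t-test. But the clause has no rule for when it applies, and Wilcoxon does not cure unequal spread at 40/20. With normal data and equal centres its type I error was 5.9%, 6.9% and 8.3% when the Rapamune SD was 1.25, 1.5 and 2 times larger, and 4.1%, 3.5% and 3.2% in the reverse case.

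A third is that Welch is not free. On untransformed skewed data this stands, as the 80.5% v 73.7% comparison shows. The log scale removes that loss, and for purely proportional spread it does most of the work.

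Last, the study is declared exploratory and "therefore not powered to show statistical difference". That lowers the stakes. It does not make the pooled test the right one.

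**Conclusion.** The point holds as a minor one. At 40:20 the specified test is miscalibrated whenever the arms differ in spread. Assuming normal data, equal means and a two-sided 5% level, type I error is about 3.6% to 6.8% for SD ratios of 0.8 to 1.25. The extremes of 1.8% and 11.1% require a twofold difference in SD, which is an assumption and not a figure from the plan. Where spread merely follows the mean, the consequence is gained or lost power, depending on which arm is higher.

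A reader might go further and conclude that the trial's conclusions are at risk, or that every continuous outcome is affected. The documents support neither. The primary endpoint combines graft survival and biopsy-proven rejection and is not tested by t-test. Only secondary and exploratory outcomes that are analysed by t-test are exposed, and nothing in the plan indicates that estimated GFR, white cells or platelets will differ in spread between arms.

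**What to change.** In the synopsis (Data analysis) and in Sections 10.1.2 and 10.2.1:

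- Replace Student's t-test with Welch's unequal-variance t-test.
- Analyse right-skewed outcomes, triglycerides and creatinine in particular, on the log scale.
- Make the synopsis match Section 10, including whether Wilcoxon is used and for which named outcomes.

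The cost is a few lines of text, with no change to design, sample size or patient care. The power lost is under 1 percentage point when the SDs are equal on the analysis scale. Welch on untransformed skewed data can lose more and leaves some type I error uncorrected, so the log scale should be adopted together with it.

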6.3 Treatment assignment

Randomization will be stratified by type of donor kidney received (living or deceased donor kidney) and primary versus retransplant recipient. Randomization will be performed using a random number generator.

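### Randomisation is stratified by donor type, but every planned comparison is pooled, so a chance donor-mix imbalance would go uncorrected if assignment is not blocked (minor)

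*Combined protocol and SAP*

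**What the plan says.** Section 6.3 (Treatment assignment): "Randomization will be stratified by type of donor kidney received (living or deceased donor kidney) and primary versus retransplant recipient". The mechanism given there is "Randomization will be performed using a random number generator". Section 5 (Population) adds "We will randomize 2:1 Zortress to Sirolimus using a random number generator" and "We would propose to enroll a total of 60 patients over 12 months". Neither place mentions blocks or minimisation.

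The analysis text does not use the strata. Section 10.1.2 has "dichotomous variables evaluated by Chi-Squared analysis, continuous variables by Student's T-Test" and, for time to event, "Kaplan-Meier survival curves with log rank tests will be used to determine a difference in graft and patient survival over time". Section 10.2.1 repeats this for the secondary endpoints, and the Data analysis paragraph of the synopsis says "Patient and graft Kaplan-Meier survival curves will be compared by log rank test". No stratified or covariate-adjusted comparison is named in any section.

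Two other places matter. Section 1 (Background) gives the only event rate: "our acute rejection rate within the first year post-transplant has been between 7% and 10% for any given calendar year". On eligibility, the synopsis and Section 5.1 (criterion 2) restrict inclusion to primary recipients, while the Study design text (Section 4) and Section 5 admit retransplants. The second stratification factor may therefore have an empty level.

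**The concern.** Donor type was judged prognostic enough to stratify on, and Section 5 puts the centre's mix close to even (100 to 110 living and 90 to 100 deceased donor transplants a year), where a binary factor varies most. If the arms differ in donor mix by chance, a pooled table or unstratified log-rank test attributes the resulting outcome difference to the drug. No planned analysis would reveal or remove it, and an adjustment chosen after seeing an imbalance is less credible than one fixed beforehand. Section 6.5.6 gives this some practical weight, because it makes a statistically significant difference in the primary outcome a trigger for considering early termination.

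**Working it through.** The plan states no power, effect size, alpha or donor-specific event rate, so there is no figure of its own to reproduce.

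**Inputs from the documents.** 60 patients at 2:1, so about 40 v 20; donor mix close to 50:50; first-year acute rejection 7% to 10%, which is 60 x 0.07 = 4.2 to 60 x 0.10 = 6.0 events. The composite also counts graft loss and death, so its rate will be somewhat higher.

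**Assumptions not in the documents.** Two-sided 5% level; donor-specific control event rates as listed in the table; treatment odds ratio 4 in both donor types when power is computed.

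**Step 1: size of a chance imbalance.**
- Unblocked: SD = sqrt(0.25 x (1/40 + 1/20)) = sqrt(0.01875) = 13.7 points. By the normal approximation, P(gap of 20 points or more) = 2 x (1 - Phi(0.20/0.137)) = 14%. Simulating 30 living and 30 deceased recipients, each assigned with probability 2/3, gives an SD of 14.0 points and a gap of at least 20 points in about 16% of trials.
- Blocks of 6 within the four strata (retransplant share assumed 15%): SD about 4 points, and no simulated trial reached a 20-point gap.

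**Step 2: what a 20-point gap does to the estimate.** Shift = gap x (deceased-donor risk - living-donor risk); SE = sqrt(p(1-p)(1/20 + 1/40)).
- Overall risk 10%, donor odds ratio 2 (7.1% v 13.2%): shift 0.20 x 6.15 = 1.2 points.
- Overall risk 10%, donor odds ratio 3 (5.5% v 14.9%): shift 0.20 x 9.4 = 1.9 points. For both, SE = sqrt(0.09 x 0.075) = 8.2 points.
- Overall risk 15% (8% v 22%): shift 0.20 x 14 = 2.8 points, SE = sqrt(0.1275 x 0.075) = 9.8 points.

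**Step 3: power with balanced strata.** Fix 20 v 10 patients in each donor type and sum the product of four binomial probabilities over all outcomes in which the test rejects. The Cochran-Mantel-Haenszel (CMH) test is asymptotic, without continuity correction, with two donor-type strata. The exact stratified test orders outcomes by conditional probability.

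| Control rates, living/deceased | Pooled chi-squared | CMH | CMH minus pooled | Exact stratified |
|---|---|---|---|---|
| 7%/10% | 37.9% | 37.3% | -0.7 | 34.6% |
| 6%/14% | 40.8% | 41.2% | +0.4 | 37.0% |
| 8%/22% | 51.5% | 52.5% | +1.0 | 46.3% |
| 10%/40% | 52.9% | 59.4% | +6.5 | 52.8% |

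(Differences are taken before rounding.) With unblocked assignment (400,000 simulated trials per row), pooled v CMH power is 37.6 v 36.3%, 40.1 v 40.2%, 49.3 v 50.9% and 51.1 v 57.2%. The exact stratified test falls below CMH by 2.7, 4.2, 6.2 and 6.6 points.

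**Step 4: false positives under no treatment effect.** With balanced strata, all three tests stay below 5%. Over all unblocked trials the pooled test rejects in 4.0%, 4.3%, 4.9% and 5.2% (rows in the same order). Among unblocked trials with a gap of at least 20 points, pooled v CMH gives 4.0 v 4.0%, 4.9 v 4.3%, 6.1 v 4.8% and 8.7 v 4.9%.

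**Step 5: log-rank.** The available simulation covers 1 year only and stratifies by all four cells (10% control risk, hazard ratio 4, 4,000 trials per scenario). Plain v stratified power at donor hazard ratios 1, 2 and 3 is 52.1 v 51.2%, 51.5 v 51.8% and 48.1 v 50.2% blocked, and 52.7 v 50.0%, 49.8 v 48.5% and 47.7 v 48.2% unblocked. No donor-type-only or 3-year log-rank calculation was made.

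**The case against.** The strongest reply is that stratified randomisation already deals with donor mix. With blocks inside strata the imbalance is about 4 points and the pooled tests are, if anything, slightly conservative. This stands: the imbalance concern is conditional on unblocked assignment. But stratifying without a restriction inside the strata balances nothing, and a random number generator is the only mechanism described.

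It can also be said that the bias is small beside the sampling error, that few events are expected, and that Sections 10.3 and 10.4 call the study exploratory and unpowered. All of that stands and sets the priority. Section 6.5.6 also leaves the reading of any difference to the treating physicians, so a false signal would not by itself stop the trial.

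A reader might infer more than the documents support:
- *The pooled tests give up material precision.* Only the 10%/40% scenario shows this. It implies about 25% overall in controls, against a documented rejection rate of 7% to 10%. Enrolment also favours patients with expected good early function, which may narrow the donor gap.
- *The gain grows by year 3.* The documents give no donor-specific survival figure, and nothing was computed at that horizon.
- *The pooled tests are invalid.* Averaged over trials, their error rate stays near or below 5%. The excess appears only in the badly imbalanced trial, and then only if donor types differ appreciably.

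**Conclusion.** The mismatch is real: the trial randomises by donor type and no planned analysis uses it. Its main consequence is an uncorrected chance imbalance, plausible only if assignment is unblocked (20 points or more in about 16% of such trials), with a shift of about 1 to 3 percentage points for a 20-point gap. The power effect at 1 year is negligible, about -1 to +2 points in the three lower-rate scenarios, and sizeable only if donor types differ widely. These sizes rest on the assumed donor rates and the assumed odds ratio of 4. Stratifying by donor type is still the better primary choice, since it follows the design at almost no cost and holds the error rate below 5% in the unlucky trial. Minor priority in an exploratory pilot.

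**What to change.** - In Section 10.1.2, Section 10.2.1 and the synopsis, specify the binary comparisons as a Mantel-Haenszel risk difference with the asymptotic, uncorrected CMH test, stratified by donor type. Specify the log-rank tests as stratified by donor type. Report the pooled results as a check.
- Do not use an exact stratified test for this purpose: it costs about 3 to 7 power points against CMH in the table above.
- In Section 6.3, state whether assignment is blocked within strata and how.
- Reconcile the eligibility passages on retransplants (synopsis inclusion criteria and Section 5.1 against Sections 4 and 5). Until then, leave primary/retransplant out of the stratified analysis; four strata are too sparse for the few events expected.

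The cost is a few sentences. No new data are needed, because donor type is recorded at randomisation.
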